10.1	Subgroup analyses.....	28

10.2	Breastfeeding.....	29
11	Implementation of the Analysis Plan.....	29
12	References.....	29
13	Appendix	32
A.	Appendix A Dummy Tables	32
i.	Participant flow	32
ii.	Baseline characteristics	33
iii.	Analysis of primary outcomes results	36
iv.	Analysis of secondary outcomes results.....	40
v.	Subgroup analysis results	42
vi.	Safety analysis results.....	43
vii.	Adherence to intervention.....	44

List of abbreviations used

AE	Adverse Event
ASQ:SE-2	Ages and stages questionnaire: social and emotional, 2 nd edition
CI	Confidence Interval
CTRU	Clinical Trials Research Unit
DMEC	Data Monitoring and Ethics Committee
E-SEE	Enhancing Social and Emotional health in the Early years
FU	Follow-up
ICC	Intraclass Correlation Coefficient
IQR	Inter Quartile Range
ITT	Intention to treat
IY	The Incredible Years programme
IY-I	Incredible Years Infant programme
IY-T	Incredible Years Toddler programme
LA	Local Authority
NIHR	National Institute for Health Research
PHQ-9	Patient Health Questionnaire
RCT	Randomised Controlled Trial
SAE	Serious Adverse Event
SAP	Statistical Analysis Plan
SAU	Services as usual
SD	Standard Deviation
SE	Standard Error
SOP	Standard Operating Procedure
TMG	Trial management group
TSC	Trial steering committee

Summary table

Trial title	Enhancing Social-Emotional Health and Wellbeing in the Early Years (E-SEE): A Community-based Randomised Controlled Trial and Economic Evaluation of the Incredible Years Infant and Toddler (0-2) Parenting Programmes
Trial design	A parallel, two arm, individually randomised controlled trial. Participants randomly allocated to intervention or control in a 5:1 ratio. Intervention parents receive an IY-B book (universal level). Dependent on level of need at data collection points 2 and 3, intervention parents may be invited to join a IY-I programme (10 weeks; 2 hours/ week) and/or IY-T (12 weeks; 2 hours/ week). Control parents receive services as usual. IY-I and IY-T are not offered as part of SAU in participating LAs.
Trial participants	Parents of children aged 0 to 2 months at baseline, identified by children's centre staff, self-referral, Health Visitors and parent advisory committee. Level of need is assessed by completion of a self-report mental health questionnaire (parent) and a parent-report measure of child social and emotional development. Co-parents are included in measure completion (and in parent programmes if parent is allocated to intervention condition at each level of intervention dose).
Sample size	606 participants allocated in a ratio of 5:1 (intervention:control)

Follow-up	Measures are administered during home or community based visits at four intervals; baseline and three follow-ups (2, 9 and 18 months post baseline assessment).
Primary analysis	Repeated measures analysis on ASQ:SE-2 scores, comparing treatment and control groups to investigate the effectiveness of the proportionate delivery of the IY E-SEE steps/model overall on child social and emotional wellbeing.
Key Secondary analyses	Repeated measures analysis on PHQ-9 scores, comparing treatment and control groups to investigate the effectiveness of the proportionate delivery of the IY E-SEE steps/model overall on parent depression levels

1 Introduction

This document outlines the detailed statistical analysis plan (SAP) for the E-SEE main trial and is intended to be read in conjunction with the current study protocol (v10. This SAP is written in conjunction with the International Conference on Harmonisation topic E9 (ICH E9 Expert Working Group, 1999), guidance for the content of SAPs in clinical trials (Gamble *et al.*, 2017), applicable statistical standard operating procedures (SOPs) from the University of Sheffield Clinical Trials Research Unit (CTRU) and trial documents (Protocol and Data Validation Specification). The trial is conducted in accordance with Good Clinical Practice in Clinical Trials (ICH Harmonised Tripartite Guideline, 1996) and Medicine for Human Use (Clinical Trials) Regulations (UK Statutory Instruments, 2004).

This SAP will guide the Trial Statistician during the statistical analysis of all quantitative outcomes in order to answer the objectives of the study. It excludes the health economic and process evaluations (which will be described elsewhere).

All analysis will be performed in a validated statistical software package such as R (Team, 2012).

1.1 Study Outline

E-SEE is a community based randomised controlled trial (RCT) designed to assess the effectiveness of the Incredible Years (IY) parent programme when compared to service as usual (SAU). The IY intervention comprises of three levels: the Incredible Babies book, and two group-based programmes IY-Infant (IY-I) and IY-Toddler (IY-T). Detailed descriptions of these components can be found in the study protocol (v10). Control condition parents/co-parents receive SAU; IY-I and IY-T do not form part of SAU in the participating local authorities (LAs), although other parenting programmes – including IY for older children - may be available.

The E-SEE study comprises of two stages, phase 1 is an 18-month pilot study conducted in two LAs and phase 2 is a 30-month main trial conducted in four LAs. The statistical analysis of phase 1 has been outlined in a separate statistical analysis plan (see study documentation table in references section.)

1.2 Objectives

- a) Main effectiveness analyses of the intervention (compared to SAU) will be established at the follow-up 18-months post-baseline to address the key research questions relating to clinical outcomes.
- b) Economic evaluation: Establish cost-effectiveness using health, quality of life and service use data and IY intervention cost data, and explore the potential for long-term modelling of costs and benefits by extrapolating from trial outcomes.
- c) Comparative work: (1) Match and compare intervention participant outcomes with cohort general population data (e.g. Millennium Cohort Study); and (2) Conduct international comparison of outcomes with the complementary Irish trial, with IY-I and IY-T delivered in a non-proportionate universalism model, and explore potential opportunity (pending agreement from key stakeholders) to pool data from both studies to facilitate a meta-analysis.
- d) Establishing the importance of process: engagement, referral, and implementation fidelity rates will be at appropriate levels and effects of process, particularly fidelity, on outcome will be examined. Qualitative work objectives include establishing parent and co-parent perception of programmes and exploring the facilitative and inhibitive factors in service delivery.
- e) Establishing for whom the programme works best and how by exploring mediators and moderators of change.

This SAP is concerned with the main effectiveness analysis (objective A). Objective B is covered by the Health Economics Analysis; objective C is covered in an ancillary sub-study (ancillary sub-study D in the protocol); objective D is covered by the process evaluation and objective E will be covered in an additional ancillary sub-study following submission of the trial manuscript. The protocol also outlines ancillary sub-studies A to C (See page 24 in Protocol V10 11.06.2019). These ancillary sub-studies are covered in the appropriate sub-study reports.

2 Outcome measures

2.1 Primary outcome measure

The following are measured at all time-points (baseline, 2, 9, and 18 months post-baseline), unless otherwise stated:

- a) Social and emotional wellbeing – to establish effectiveness of the proportionate delivery of the IY E-SEE steps/model overall i.e. three levels of IY- the book, IY-I and IY-T, using parent report *Ages & Stages Questionnaire – Social Emotional (ASQ:SE-2)*. The co-parent is not asked to complete this questionnaire.

2.2 Secondary outcome measures

2.2.1 Child secondary outcome measures¹

The following measures are completed independently by parent and co-parent at all three timepoints unless otherwise stated.

- a) Behaviour – measured at 18-month follow-up using parent/co-parent report *Strengths and Difficulties Questionnaire (SDQ)*.
- b) Cognitive development – measured at 18-month follow-up using parent/co-parent report *PedsQL Infant Scale*.
- c) Health (quality of life) – measured at 18-month follow-up using parent/co-parent report *PedsQL Infant Scale*.
- d) Service use – using parent report: *Client Service Receipt Inventory (CSRI)*.

2.2.2 Primary care-giver and co-parent secondary outcomes

Key Secondary Outcome² for primary care-giver and co-parent

- a) Depression – to establish overall effectiveness of the IY programme, using the parent/co-parent report *Patient Health Questionnaire (PHQ-9)*.

Other Secondary outcomes for primary care-giver and co-parent

- b) Carer-child attachment/interaction – measured at 18-month follow-up using parent/co-parent report *Maternal Postnatal Attachment Scale (MPAS)* and/or *Paternal Postnatal Attachment Scale (PPAS)*.
- c) Parenting skill – using parent/co-parent report *Parent Sense of Competence (PSoC)*.
- d) Health Related Quality of Life (HRQoL) – using parent/co-parent report *EQ5D5L*.
- e) Service use – using parent report CSRI.

2.2.3 Parent-child dyad secondary outcome measures

- a) child feeding methods

¹ The original intention was to use the Eyberg child behaviour inventory. This was replaced with the SDQ in the early stages of the trial and a protocol amendment made. [See version 5 amendments in 'Protocol amendments since Version 1' in version 10 of the protocol.]

² In protocol v10 the PHQ-9 is described as the "parent and co-parent primary outcome". In the published protocol the PHQ-9 is described as the 'parent primary outcome'. These descriptions are technically incorrect because the trial is powered on ASQ-SE2 alone. PHQ-9 will be described as the key secondary outcome henceforth.

- b) Dyadic synchrony³ – using the CARE Index, observational report, solely conducted with the parent-child dyad.

3 Sample Size Estimation

A detailed description of the sample size for the E-SEE Main trial can be found in protocol v10.

4 Randomisation, Inclusion in the Intervention Arm & Blinding

4.1 Sequence generation

Randomisation is at the individual level using a web-based randomisation system developed by Sheffield CTRU in collaboration with a University spin-off company (epiGenesys) and using a randomisation sequence prepared by the trial statistician. E-SEE participants are randomised in a 5:1 ratio to intervention and control arms, stratified by:

- depression scores (PHQ-9 score ≥ 5) or child social emotional wellbeing (Child ASQ:SE2 score \geq Monitoring Zone);
- sex of child;
- sex of carer;
- recruitment site (see above).

Prior to recruitment starting a test system was made available for training purposes. Any user comments or suggestions on the usability of the system are fed back to the program developer before the system is made live.

Randomisation occurs after eligibility has been established, informed consent obtained, and baseline measures collected from parents to reduce initial attrition. The allocation schedule is concealed and the intervention arm is only confirmed once eligibility and consent are confirmed by researchers. A member of the University of York research team inputs participant information to the online system to enable randomisation, with allocation results returned immediately. The University of York trial coordinator informs families of allocation to condition.

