7.1 General Considerations

Data will be reported according to the Consolidated Standards Of Reporting Trials (CONSORT) statement for individually randomised parallel group trials (Schulz, Altman and Moher, 2010) and extension (Juszczak *et al.*, 2019).

Summaries of continuous variables will comprise the number of observations used, mean, median, standard deviation (SD), inter-quartile range (IQR), minimum and maximum as appropriate for the distribution of the data.

Summaries of categorical variables will comprise the number of observations used, and the number and percentage of observations in each category. Tables containing the results of the statistical modelling will present the overall difference between treatment groups with two-sided 95% confidence intervals (CI) and p-values. Hypothesis tests will use a two-sided 5% significance level.

Complete details of data derivations and methods for handling missing data is covered in sections 8.1 and 9.

All analyses are based on the overall score only unless otherwise stated.

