7.6 Analysis of the primary outcome

7.6.1 Primary Analysis of the primary outcome

The ASQ:SE-2 is a set of questionnaires with different versions for different age groups. Consequently, different versions will be completed at each time point. The primary analysis will use raw ASQ:SE-2 scores as the scoring is the same across treatment arms and estimates will be easier to interpret. For ASQ:SE-2 either the 2 month or the 6 month questionnaire is administered at Follow-up 1 dependent upon the developmental age of the baby. If we observe an imbalance between arms in the number receiving the 2 months and 6 months versions we will adjust the score for those receiving the 2 months version by multiplying by 1.24. We have based the adjustment on the monitoring thresholds (25 and 30 for the 2 and 6 months surveys) and referral thresholds (35 and 45 for the 2 and 6 months surveys). The adjustment is midway between those required to preserve the monitoring threshold (30/25) and the referral threshold (45/35). If participants have completed both questionnaires, we will use the 6 months version and exclude them from the potential adjustment procedure.

The overall treatment effect will be estimated using a marginal model fitted using general estimating equations to account for the repeated measures with a Gaussian family, identity link, robust standard errors and an autoregressive covariance structure of order 1 AR(1). If the model does not converge using AR (1) we will use an unstructured correlation structure. The fixed effects will be stratifying variables (baseline ASQ:SE-2 score, baseline PHQ-9 score,

site⁴ and sex of child); potential confounders (ethnicity of the primary caregiver, marital status and highest level of education and follow up time (using an indicator variable for each time point)).

- The therapist induced clustering effect will not be fitted because the offer of IY-I and IY-T is conditional on outcome at FU1 and FU2 so clustering is confounded with treatment effect leading to biased estimation of the latter.
- The repeated measurements will be accounted for using a marginal model fitted using GEE because accounting for repeated measures using a mixed model inflates the type 1 error (random intercept only model) or gives a biased estimate of the treatment effect (random intercept and slope model).

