7.7 Analysis of key secondary outcomes

The impact of the intervention on PHQ scores will be investigated using the same approach as the primary analysis of the primary outcome. Descriptive statistics will be presented for PHQ-9 at each time point (Appendix Table 6). Mean PHQ-9 scores and 95% CIs by treatment arm will be presented in line plots. Spaghetti plots will also be used to visualise individual changes over time.

The IY intervention in this trial comprises three main components – the IY-I book, IY-I and IY-T programmes. All participants who meet the eligibility requirement for being stepped up to IY-I and/or IY-T are given the opportunity to do so and there is no randomisation element in the step up. As such the following secondary analysis provides a non-randomised indicative analysis of the possible impact of individual components. The impact of individual components will be investigated using ASQ:SE-2 and PHQ-9 at the relevant follow up point with those participants in the control arm who would have been eligible for IY-I or IY-T in each case used as the control group comparator.

- Comparison between intervention and control groups at FU1 will provide an indicative analysis of IY-B;
- Comparison between intervention and control for the subgroup of parents with PHQ-9 score ≥ 5 OR Child ASQ:SE-2 score \geq Monitoring Zone at FU2 will provide an indicative analysis of IY-I;
- Comparison between intervention and control in the subgroup of parents with PHQ-9 score ≥ 5 OR Child ASQ:SE-2 score \geq Monitoring Zone at FU3 will provide an indicative analysis of IY-T.

These analyses will be conducted using multiple linear regression models including the same stratification variables (baseline ASQ:SE-2 score, baseline PHQ-9 score, sex of child and recruitment site) and potential confounders (ethnicity of the primary caregiver, marital status and highest level of education) as covariates. The mean difference, 95% confidence interval and associated p-values will be presented (Appendix Table 7).

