7.8 Analysis of other secondary outcomes

Not all secondary outcomes will be collected at all four time points. For those outcomes that have been collected at all four time points (PSoC, EQ5D-5L, CARE Index), mean scores by treatment arm will be presented in line plots (Figure 4) and the impact of the intervention on these outcomes will be investigated using the same approach as the primary analysis of the primary outcome.

For those outcomes only collected at FU3 (MPAS/PPAS, PEDSQL, SDQ), descriptive statistics will be presented by treatment arm. A multiple linear regression model will be used to estimate the adjusted mean difference between treatment arms. Stratification variables (baseline PHQ-9 score, baseline ASQ:SE-2 score, sex of child and site) will be included in the model as covariates.

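### The linear regressions in SAP 7.7 and 7.8 do not call for robust standard errors, although allocation is 5:1 and the primary GEE uses them; naming HC3 would be a free improvement.

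*SAP*

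**What the plan says.** The summary table gives 606 participants, and section 4.1 says that "E-SEE participants are randomised in a 5:1 ratio to intervention and control arms". Section 7.1 sets the test level: "Hypothesis tests will use a two-sided 5% significance level".

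Section 7.6.1 fits the primary outcome by GEE "with a Gaussian family, identity link, robust standard errors". Overall PHQ-9 (7.7) and PSoC, EQ5D-5L and the CARE Index (7.8) take the same approach, so they also get robust standard errors.

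Two sets of analyses do not:

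- **Component comparisons (7.7)**, for the book, IY-I and IY-T: "These analyses will be conducted using multiple linear regression models including the same stratification variables". They are to be reported with mean differences, 95% confidence intervals and p-values.
- **Outcomes collected only at FU3 (7.8)**, namely MPAS/PPAS, PedsQL and SDQ: "A multiple linear regression model will be used to estimate the adjusted mean difference between treatment arms".

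Neither place says whether the standard errors are model-based or robust.

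**The concern.** An unqualified linear regression will normally be run with ordinary standard errors, which assume one residual variance for both arms. With equal allocation that assumption does little harm. At 5:1 it matters: the arm that dominates the pooled variance estimate is not the arm that dominates the true variance of the difference. If controls are the more variable arm, intervals are too narrow. If the intervention arm is, they are too wide.

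Unequal spread is possible here. IY-I and IY-T are offered in the intervention arm alone, and only to families above a need threshold (4.2), so any effect is unlikely to be uniform. Appendix B also accepts that group delivery may add correlation in that arm. These two mechanisms can push the spread in opposite directions, so the sign of any error cannot be predicted from the SAP.

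At stake are the stated 95% and 5% properties of the intervals and p-values for attachment, quality of life, behaviour and the component comparisons. Leaving the choice open also means it is made after unblinding.

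**Working it through.** **Inputs from the SAP.** Total 606 at 5:1, so 606 × 5/6 = 505 intervention and 606/6 = 101 control; two-sided 5% level. The total of 606 itself cannot be rederived here, because the SAP leaves the sample size calculation to the protocol.

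**Assumption.** The ratio r = residual SD in control ÷ residual SD in intervention. The SAP gives no SDs by arm, so a range is shown.

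**Which arm carries the weight.**

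- Share of the true variance from control, at equal SDs: (1/101) / (1/101 + 1/505) = 0.833.
- Weight of the intervention arm in the pooled variance: 505/606 = 0.833.

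**Formulae** (k = 5, intervention SD set to 1, common factor 1/101 dropped):

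- variance assumed by ordinary least squares: V_ols = [(k + r²)/(k + 1)] × (1/k + 1)
- true variance: V_true = 1/k + r²
- q = √(V_ols / V_true)
- actual type I error = 2 × [1 − Φ(1.96 q)]

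| r | V_ols | V_true | q | Type I error at 5:1 | At 1:1 |
|---|---|---|---|---|---|
| 0.8 | 1.128 | 0.840 | 1.159 | 2.3% | 5.0% |
| 0.9 | 1.162 | 1.010 | 1.073 | 3.6% | 5.0% |
| 1.0 | 1.200 | 1.200 | 1.000 | 5.0% | 5.0% |
| 1.1 | 1.242 | 1.410 | 0.939 | 6.6% | 5.0% |
| 1.25 | 1.3125 | 1.7625 | 0.863 | 9.1% | 5.0% |

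**Simulation check** (unadjusted; 10,000 runs at 505:101, 20,000 at smaller sizes). At 505:101 ordinary intervals covered 97.7% at r = 0.8 and 90.7% at r = 1.25, in line with the table. With HC3, over r from 0.67 to 1.5, coverage was 94.6–95.0% at 505:101, 94.7–95.0% at 150:30 and 94.2–95.0% at 75:15. The smaller sizes stand in for the need subgroups, whose actual size the SAP does not give.

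**Appendix B's own inputs.** SD 10, correlation 0.4, overall effect 3.46, effect 2.5 at FU1 and 15 for those stepped up at FU2. Both readings below take 3.46 as the mean of the FU1 and FU2 effects, and step up the fraction p with the highest FU1 scores.

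- *Reading A: families not stepped up keep 2.5 at FU2.* p = (2 × 3.46 − 5)/12.5 = 0.154, which matches the 76 places in the 13 listed groups if about 495 are in the arm (76/0.1536 ≈ 495). Intervention variance at FU2 = 100 + 12.5² p(1 − p) − 2 × 12.5 × 0.4 × 10 × φ(1.021) = 100 + 20.3 − 23.7 = 96.6, SD 9.83. Then r = 1.017 and type I error is 5.3%.
- *Reading B: families not stepped up have no effect at FU2.* p = (2 × 3.46 − 2.5)/15 = 0.295. Variance = 100 + 15² p(1 − p) − 2 × 15 × 0.4 × 10 × φ(0.540) = 100 + 46.8 − 41.4 = 105.4, SD 10.27. Then r = 0.974 and type I error is 4.6%.

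Either way the departure from 5% is under 0.5 percentage points, and its sign depends on the reading.

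**The case against.** **The premise is an inference.** A reader might take the SAP to prescribe model-based standard errors. It does not; it is silent, and ordinary least squares is only the default reading. Nor is all of 7.7 and 7.8 exposed, since overall PHQ-9, PSoC, EQ5D-5L and the CARE Index use the robust GEE. Both points stand and limit the scope.

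**There is no evidence of unequal spread.** With no SDs by arm, the 6.6% and 9.1% figures are conditional, and on Appendix B's inputs the error is negligible. Any undercoverage from a programme that helps only needy families also depends on how the scenario is built. At 505:101 with baseline adjustment, defining need as the top 30% of a normal baseline score gave 95.1–95.7% coverage. Treating need as a separate 30% subpopulation gave 92.6–94.8%. This stands: the documents do not support saying that the intervals are wrong, only that they are unprotected.

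**The mechanisms reach the component comparisons weakly.** FU1 precedes any group programme. In the IY-I and IY-T comparisons both arms are restricted to families meeting the need criterion, so the threshold alone does not compress one arm. Section 7.7 also calls these comparisons non-randomised and indicative. This stands as a limit on importance, although they will still carry intervals and p-values.

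**Should the standard errors also be clustered by group?** A reader might infer this, because 7.6.1 gives a reason that concerns fitting an effect: "The therapist induced clustering effect will not be fitted because the offer of IY-I and IY-T is conditional on outcome at FU1 and FU2". A correction to the standard error alone would leave the estimate unchanged. But Appendix B reports that such corrections were examined for linear regression. Cluster-robust standard errors always over-controlled type I error, and naive regression did best for ICC below 0.1, because group correlation is confounded with selection. The documents therefore do not support asking for a cluster-robust or cluster-jackknife version. That evidence concerns clustering under targeted selection; it does not address unequal arm variances at 5:1, so it leaves HC3 untouched.

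**Conclusion.** The point holds in a limited form. The SAP protects the GEE analyses with robust standard errors and leaves the linear regressions without them, with no reason given, in a design where 5:1 allocation removes the usual robustness to unequal variances. Under the default reading, type I error runs from about 2.3% to 9.1% for assumed control:intervention SD ratios of 0.8 to 1.25. It is within 0.5 points of 5% on Appendix B's inputs. The figures rest on an unadjusted large-sample formula, confirmed by simulation, and on SD ratios that the SAP does not supply.

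The primary analysis and overall PHQ-9 are not affected. This is a free improvement to secondary and indicative analyses, not a demonstrated error in their results.

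**What to change.** Add one sentence to 7.7 and one to 7.8: *Standard errors of all linear regressions will be heteroscedasticity-robust (HC3), consistent with the robust standard errors of the primary analysis.* Point estimates, covariates and populations stay as planned, and no clustering adjustment is requested.

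The cost is a software option; no new data are needed. If the spreads are in fact equal, almost nothing is lost: simulated coverage at r = 1 was 94.8% with HC3 against 95.0% with ordinary standard errors at 505:101, and 94.7% against 94.9% at 75:15. Making the change before unblinding also removes an analyst's choice.
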